### Risks

The medical risks are described in the adverse event section. Other risks related to the loss of confidentiality are described in the confidentiality section with steps we will take to mitigate any such risk.

*Participant Burden:* Participation in this protocol will require moderate subject time and effort. Therefore, in addition to recommended safety measures described below, additional efforts will be taken to minimize subject burden and maximize retention throughout the study. It is of note that our study team has a strong track record of successful clinical research requiring similar participation and retention has been high in these efforts.

Several strategies will be employed to minimize subject burden and maximize adherence to the protocol.

Specifically we will:

- Develop a personal relationship between subjects and members of the staff by matching research assistants with individual participants.
- Schedule appointments at convenient times with familiar staff.
- Explain to subjects all aspects of their participation.

- Provide reminders of all appointments.
- Include personal notes in the subject's data file to remember events in the life of the participant; these can be commented on at future visits (e.g. birth of a grandchild)

Any participant who suffers an adverse event during the conduct of study protocols will be triaged immediately by the medical investigators, and the study psychiatrist. The study PI and study psychiatrist will monitor and manage all study related A/E's. If follow up care is needed to treat an A/E, the investigators will arrange to have this care provided at a nearby institution, convenient to the study participant. . The treating provider will bill the insurance company or other third parties, if appropriate, for the care a participant receives for any injury. We will try to have these costs paid for, but the participant may be responsible for some of them. For example, they may be responsible for payment of any deductibles and co-payments required by the insurer. There are no plans to provide any compensation for an injury beyond what is described above, should one occur.

If there is a change in the clinical condition of the participant, the study psychiatrist will contact the subject's treating/primary psychiatrist so that appropriate primary clinical care can be provided.

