### Visits (All visits will be conducted remotely)

For this study, participant caregiver administrators will be provided remote step-by-step training to administer the tDCS sessions to the participants with MDD. Participant caregiver-administrators will be directly supervised remotely, until they demonstrate proficiency, without coaching by the study team. We have developed a step by step training manual, and have successfully trained older adult caregivers to administer the tDCS.

Visit	Purpose	Procedures	Study personnel	Duration	Location
Pre-ICF	Advance review	Informed consent pre-review by potential participants	RA will send	As needed for review	Mailed/emailed to P
Visit 1	Remote screen and assessment visit	Informed consent [ P with MDD ] Mental Health/Medical health history; medications; Cognitive Assessment; Interview with study psychiatrist [ Participant caregiver-administrators ] Health history; computer proficiency questionnaire [ Both participants ] tDCS overview and training	Study research assistant; Study psychiatrist	~ 1 hour	Remote
Home tDCS administration Treatment period – Daily tDCS sessions over 4 weeks *Participant ratings of suicidality will be completed each day, and responses will be monitored and immediately be reviewed in real time by the study RA and study psychiatrist. Any changes from baseline will result in an immediate contact to the participant by the study psychiatrist.					
Week (Wk)1; Day (D) 1	Home-based tDCS	At-home tDCS equipment set-up; tDCS administration by caregiver-administrator with step-by- step remote training by study staff Daily diary	Study research assistant	1 hour total (tDCS session=30 mins)	Video conference
Wk1, tDCS session	Home-based tDCS once a day	tDCS admin by the caregiver-administrator with remote staff oversight and coaching Daily	Study research assistant	1 hour total (tDCS session=30)	Video conference

D 2-4		diary		mins)	
Wk 1, tDCS session D 5	Home-based tDCS	tDCS admin by the caregiver-administrator with remote staff oversight and coaching; Staff administered skills test for caregiver-administrators Daily diary	Study research assistant	1 hour total (tDCS session=30 mins)	Video conference
Wk 1-4; D6-28	Home-based tDCS once a day	The caregiver-administrator will administer the in-home tDCS session with remote staff monitoring and video conferencing if necessary Daily diary	Study research assistant	1 hour	Participant's Home

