Wks 1-4, D 7, 14, 21, and 28	Weekly assessments	Participants with MDD only Week 1-4 Assessment completion (Day 7, 14,21, and 28); depression symptoms and quality of life assessments	Study research assistant	30 minutes	Phone
Home tDCS administration Treatment taper period – weeks 5-8 Participant ratings of suicidality will be completed each day, and responses will be monitored and immediately be reviewed in real time by the study RA and study psychiatrist. Any changes from baseline will result in an immediate contact to the participant by the study psychiatrist.					
Wk 5, D 30,32,34	Home-based tDCS Total of 3 sessions, one every other day over a 6 day period.	The caregiver-administrator will administer the in-home tDCS session with remote staff monitoring and video conferencing if necessary Daily diary	Study research assistant	1 hour	Participant's Home
Wk 6-7, D 37,40, 43	Home-based tDCS Total of 3 sessions, one every third day over a 9 day period	The caregiver-administrator will administer the in-home tDCS session with remote staff monitoring and video conferencing if necessary Daily diary	Study research assistant	1 hour	Participant's Home
Wk 8 D 47,51, 55	Home-based tDCS Total of 3 sessions, one every fourth day over a 12 day	The caregiver-administrator will administer the in-home tDCS session with remote staff monitoring and video conferencing if necessary Daily diary	Study research assistant	1 hour	Participant's Home

	period				
Wks 5-8 D35, 42, 49, 56	Weekly assessments	Participants with MDD only Weeks 5-8 Assessment completion (Day 35, 42,49, and 56); depression symptoms and quality of life assessments	Study research assistant	30 minutes	Phone
Home tDCS administration completed after Week 8, Day 55 session. Return of Home tDCS equipment to research team in the provided shipping materials and label.					
Four week follow-up period – weeks 9-12					
Wks 9- 12 D57-84	Four week follow-up period	Participants with MDD only The study research assistant will maintain weekly contact with the participant over the 4 week follow-up period	Study research assistant	20 minutes	Phone
Week 12, Day 84	Final study assessment	Both participants: Final assessment completion, depression symptoms, quality of life assessments, cognitive assessment	Study research assistant	1 hour	Phone
End of study: Results sent to participant with MDD and treating psychiatrist					

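### The visit schedule sets a daily suicidality rating with study psychiatrist review for weeks 1–8, but states neither for the weeks 9–12 follow-up

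*Combined protocol and SAP*

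**What the plan says.** The table under Visits in the combined protocol and SAP has three periods.

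- **Treatment, weeks 1–4.** The period header states: "Participant ratings of suicidality will be completed each day". Responses go straight to the research assistant and study psychiatrist for review, and "Any changes from baseline will result in an immediate contact to the participant by the study psychiatrist".
- **Taper, weeks 5–8.** The header repeats the block: "weeks 5-8 Participant ratings of suicidality will be completed each day", with the same review and the same contact rule.
- **Follow-up, weeks 9–12.** The header carries no such block. For Days 57–84 the table says "The study research assistant will maintain weekly contact with the participant over the 4 week follow-up period": a 20-minute phone contact with no listed content. The Day 84 row lists "Final assessment completion, depression symptoms, quality of life assessments, cognitive assessment". The research assistant is the only person named in either row.

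Depression scales are listed weekly up to Day 56 ("Weeks 5-8 Assessment completion (Day 35, 42,49, and 56); depression symptoms and quality of life assessments") and next on Day 84. The table closes with "End of study: Results sent to participant with MDD and treating psychiatrist".

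Outside the table, the Risks section provides: "If there is a change in the clinical condition of the participant, the study psychiatrist will contact" the participant's own psychiatrist. A Suicide Risk Assessment Protocol appears by title in the list of forms under Data storage and confidentiality. Its content is not in the documents supplied.

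**The concern.** Followed as written, monitoring drops in one step at the end of week 8, from a daily rating seen by a psychiatrist to no scheduled suicidality rating, while participants are still in the study. They entered with a MADRS of at least 20, a medication-resistant episode, and a psychiatrist who considers TMS or ECT indicated.

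At stake is whether the study team would learn promptly of suicidality that emerges or worsens after stimulation stops. Before Day 84 it would do so only if the subject came up on a weekly call, or if the participant, caregiver or treating psychiatrist reported it. Safety is named in the primary objective, although that objective is worded around the stimulation sessions.

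**Working it through.** The plan gives no figure to reproduce. The check compares the three periods and counts days.

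**1. The periods side by side (Visits table)**

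| | Weeks 1–4 | Weeks 5–8 | Weeks 9–12 |
|---|---|---|---|
| Suicidality rating | daily | daily | none stated |
| Study psychiatrist review | yes | yes | none stated |
| Contact rule on change from baseline | yes | yes | none stated |
| Scheduled contact | sessions, weekly assessment | sessions, weekly assessment | weekly call, Day 84 assessment |

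**2. Does the end of stimulation explain the difference?** The table puts taper sessions on Days 30, 32, 34, 37, 40, 43, 47, 51 and 55, which is 9 of the 28 taper days. The rating is still required every day, so it is required on 28 − 9 = 19 days without stimulation. The rating is not tied to sessions, and the absence of sessions in weeks 9–12 does not by itself account for its absence there.

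**3. Extent in days**
- Rating stated: Days 1–56 = 56 days.
- No rating stated: Days 57–84 = 28 days; 28/84 = 33.3%.
- The text below the table runs the taper to Day 60. If the rating runs that far, 84 − 60 = 24 days; 24/84 = 28.6%.

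**4. Scheduled routes to the study team on Days 57–83**
- The email notice of adverse events (Stimulation Stopping criteria) covers events reported during a stimulation session. The last session in the table is Day 55.
- No depression scale is listed between Day 56 and Day 84.
- That leaves the weekly call. Anything else depends on an unprompted report.

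**5. What the proposed change does.** Four weeks of weekly contact give 4 ratings per participant, taking the fourth on Day 84. That is one every 28/4 = 7 days, where none is now stated. With the planned 50 participants all retained (an assumption), 4 × 50 = 200 ratings. The count of unrated days would fall only from 28 to 28 − 4 = 24, so the day share describes how long the gap is and not the benefit of closing it.

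**The case against.** The case against rests on four arguments.

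- **An unseen document.** The Suicide Risk Assessment Protocol is the natural home for follow-up procedures, and the weekly call may cover suicidality without the table saying so. This stands as a limit on the conclusion: the supplied text shows no scheduled rating, and does not show that none will be taken.
- **Other safeguards.** High suicide risk is excluded at baseline by the study psychiatrist. The primary psychiatrist must judge the patient stable enough to stay at home and must continue to follow them, and an adult lives with them (Study objectives; Eligibility Criteria). The Risks section provides immediate triage of adverse events by the medical investigators and study psychiatrist, contact between psychiatrists on a change in condition, and advice to seek care for an urgent need. Investigators review adverse events (Stimulation Stopping criteria). The triage and contact steps are not limited to weeks 1–8. All of this stands. But the baseline checks come before treatment, and the study's own later steps act only once a change is known.
- **A defensible design choice.** Clinical care never passes to the study, so stepping back to the treating psychiatrist after stimulation is reasonable. Agreed, but the table does not say that this is the intention, and it lists results going to that psychiatrist at the end of the study.
- **No sign that the end of stimulation is a risk point.** The protocol cites continued improvement after treatment, and its remark on relapse concerns older age, not stopping tDCS. I do not rely on the relapse remark. The continued improvement is a group result and does not exclude worsening in individuals.

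A reader might infer that participants have no suicide-risk protection after Day 56, or that the study psychiatrist's role ends there. The safeguards above contradict both readings.

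**Conclusion.** The point holds as a gap in the schedule. For weeks 9–12 the supplied text sets no suicidality rating and no study psychiatrist review, after setting both throughout weeks 1–8. The gap covers 28 of 84 days (33%), or 24 days (29%) if the rating follows the taper to Day 60.

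This assumes that the visit table is where rating times are set, and that the unsupplied Suicide Risk Assessment Protocol does not add a rating in follow-up. If it does, only a cross-reference is missing.

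The documents give no rate of suicidality for this window, so no number of missed events can be stated. The change is worth making because it is cheap and concerns patient safety.

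**What to change.** Add to the weeks 9–12 row: *The suicidality rating used in weeks 1–8 is taken at each weekly call and on Day 84. The study psychiatrist reviews it the same day, and the weeks 1–8 contact rule applies.* Daily ratings are not needed in this period.

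If the sponsor prefers the treating psychiatrist to take over monitoring, the row should say so. The Day 56 suicidality rating and depression score should then go to that psychiatrist at Day 56, with the participant's permission. If the Suicide Risk Assessment Protocol already covers Days 57–84, a reference to it in the row is enough.

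The cost of the first option is four short ratings per participant at contacts already planned, with no new visit, plus a modest amount of study psychiatrist time for same-day review and any contacts over four more weeks.

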## Statistical Methods and Analysis

### *Primary*

Feasibility and tolerability/safety will be evaluated using home-based data as it is collected by reported number of aborted sessions.

The *primary outcome* will be change in the observer rated MADRS score from baseline to the 1-month follow-up.

Clinical response is defined as  $\geq 50\%$  improvement in MADRS score from baseline to the 1-month follow-up. Remission is defined as a MADRS score  $\leq 10$ .

The *secondary outcome* measures will include the participant-rated Quick Inventory of Depressive Symptomatology (QIDS-SR) (Rush et al., 2003) and the Quality of Life Enjoyment and Satisfaction Questionnaire Short Form (Q-LES-Q-SF) (Endicott et al., 1993), both administered at the same time points as the MADRS. A computer-based cognitive test battery, CogState (<https://www.cogstate.com>), will provide an additional safety outcome measure. This battery includes tests designed to assess verbal learning and memory (International Shopping List Task), attention and psychomotor function (Detection Task), visual attention (Identification Task), visual learning and memory (One Card Learning Task), working memory (Two Back Task), and executive function (Set Shifting Task).

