### **Study objectives:**

**Primary objective:** Demonstrate that remote tDCS sessions applied by a caregiver are feasible, complied and adhered to, and are safe in individuals with severe depression

**Secondary objective:** Gather pilot data on the potential of home-based tDCS to induce clinically meaningful improvements in the severity of depression in individuals who would otherwise be offered rTMS or ECT treatment.

The ultimate goal of this work is to prepare the path for a subsequent randomized clinical trial to assess the antidepressant therapeutic efficacy of home-based tDCS. We thus propose a study of tele-health supervised, caregiver-delivered, home-based tDCS for antidepressant treatment of patients with a medication-resistant depression episode of uni- or bi-polar Major Depression who would otherwise qualify for rTMS or ECT.

Specifically, in the present protocol we seek to offer participation to:

- Patients with medication-resistant MDD who have undergone rTMS or ECT and responded to it but whose benefit has lapsed, and they need repeat a rTMS or ECT course that they cannot access
- Patients with medication-resistant MDD who are undergoing rTMS or ECT and responding, but cannot continue to get the rTMS or ECT course due to COVID-19 pandemic-related regulations or other access concerns
- Patients with medication-resistant MDD who are referred to rTMS or ECT and are found well qualified but cannot access rTMS or ECT due to COVID-19 pandemic-related regulations or other access concerns.

The benefits of this project address a present need due to the COVID-19 pandemic, but also go beyond the present situation and address a larger, pre-existing need.

Across all these potential groups of participants, prospective participants will:

1. Need to have a primary psychiatrist who agrees to their participation in the study and is willing to continue to follow the patient and work collaboratively with the study team
2. Need to be assessed by their primary psychiatrist to be stable enough to be able to remain at home and participate in the present study without undue risk to their safety
3. Need to be living with an adult willing and capable to provide oversight and learn to deliver the home-based tDCS
4. Have the capability to connect with the study team for daily supervision of the intervention sessions and close safety monitoring, and be willing to commit to doing so

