Daily sessions (28 daily sessions): The device will be used to apply 20 minutes of tDCS to the participant with MDD's scalp in each of 28 daily sessions.

Thereafter, participants with MDD will undergo a taper phase of an additional 9 sessions of tDCS applied in progressively decreasing frequency until day #60 of the study as follows:

- (1) First taper phase: three 30 minutes tDCS sessions applied every other day;
- (2) Second taper phase: three 30 minutes tDCS sessions applied one every third day;
- (3) Third and final taper phase: three final 30 minutes tDCS sessions applied one every fourth day.

The study team will predetermine, with the participant team, their most convenient two hour window for the home administration. During remote tDCS administration, the study team will be notified electronically by email when the tDCS session has been started and also when it has been completed, or if the tDCS session was aborted, or not completed during the predetermined two hour window.

The device will contain a sequence of simplified screen prompts for the participant,. To move to the next screen the participant will press a circle on the screen to continue (or to stop)

For example:

1. Hello
2. Battery status is GOOD
3. Today is Monday (date) It is now ( ) o'clock
4. Wear the Cap

5. Check the electrodes - 1 green is in the 1 green hole and secure, 2 yellow is in the 2 yellow hole and secure.
6. Are you ready for your 30 minutes session? If yes, press continue
7. Session has started, please stay in place until session is over [clock appears on screen to count down the minutes]
8. Session has ended, please stay in place while the device powers off.
9. Session is now completed! You may turn off the tablet, and remove the cap and electrodes

Daily sessions (28 daily sessions): The device will contain a block that will only allow one session to be administered within a 24 hour period. If a session is started and aborted, the participant will not be able to administer a new session until the next day, 24 hours later.

During the taper phase - the device block will only allow:

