First taper phase: Three sessions, one every other day. If a session is started and aborted, the participant will not be able to administer a new session until 48 hours later. After the 3 sessions have been administered, (which will include any session that was started and aborted), a new session will not be available until the next scheduled session. The study team will monitor participant study adherence through completed sessions and through video conferencing and telephone contact.

Second taper phase: Three sessions, once every third day. If a session is started and aborted, the participant will not be able to administer a new session until 72 hours later. After the 3 sessions have been administered, (which will include any session that was started and aborted), a new session will not be available until the next scheduled session. The study team will continue to monitor participant study adherence through completed sessions and through video conferencing and telephone contact.

Third and final taper phase: Three sessions, once every fourth day. If a session is started and aborted, the participant will not be able to administer a new session until 96 hours later. After the 3 sessions have been administered, (which will include any session that was started and aborted), the sessions will be completed.

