## **Withdrawal and Stopping the study**

The criteria for discontinuing a participant's participation include the participant's request, as well as any unexpected life-threatening or potentially disabling event.

A study subject may be withdrawn from the study at any time if the study subject, the investigator, or the Sponsor feels that it is not in the study subject's best interest to continue.

All study subjects are free to withdraw from participation at any time, for any reason, specified or unspecified, and without prejudice.

Reasonable attempts will be made by the investigator to provide a reason for study subject withdrawals. The reason for the study subject's withdrawal from the study will be specified in the study subject's source documents.

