## **Stimulation Stopping criteria**

Subject stimulation will be stopped if any of the following occur during the 8-week treatment period:

- Clinician impression of substantial worsening of medical condition
- If the study subject misses more than 10 stimulation visits.

Study subjects will be withdrawn from the study for the following:

- If the study subject is not compliant with the study procedures as determined by the investigator.
- If, in the investigator's opinion, it is not safe for the study subject to continue with participation in the study.
- If the study subject is withdrawn from the study, the subjects treating psychiatrist will be notified so that arrangements can be made for continued treatment of his/her MDD.
- The study team will be notified by email immediately if the subject reports any adverse events during any tDCS stimulation session, and immediate follow up will occur.
- Any adverse events that take place during testing will be reported to the PI ([name]) and recorded in the database. Drs. [name], [name] and [name] will have primary responsibility for monitoring participant safety in the trial. The investigators will be responsible for reviewing each adverse event in a timely fashion and preparing a summary report for submission to the IRB.

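### The one stated feasibility and tolerability measure, a count of aborted sessions, misses sessions that were never started, and the statistical section plans no adherence analysis and no adverse-event table

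*Combined protocol and SAP*

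**What the plan says.** Study objectives gives the primary objective as: "Demonstrate that remote tDCS sessions applied by a caregiver are feasible, complied and adhered to, and are safe in individuals with severe depression". Efficacy is the secondary objective.

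Statistical Methods and Analysis, under Primary, has one sentence on how that objective is evaluated: "Feasibility and tolerability/safety will be evaluated using home-based data as it is collected by reported number of aborted sessions". It gives no rate, summary statistic or criterion. The same section names the CogState battery as a further safety outcome. The only analysis plan that follows is the one for efficacy (MADRS, Wilcoxon signed-rank), and then comes the sample size of 50.

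The Visits section says more about sessions. The study team is notified electronically when a session starts and when it is completed, "or if the tDCS session was aborted, or not completed during the predetermined two hour window". In the taper phases the three sessions allowed are a total "which will include any session that was started and aborted". The first taper phase adds: "The study team will monitor participant study adherence through completed sessions and through video conferencing and telephone contact".

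Stimulation Stopping criteria stops stimulation on either of two grounds: "Clinician impression of substantial worsening of medical condition", and "If the study subject misses more than 10 stimulation visits". It separately lets the investigator withdraw a participant judged not compliant. Adverse events are recorded and graded for severity and relatedness (Adverse Events), and are reviewed and summarised for the IRB (Stimulation Stopping criteria).

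**The concern.** Adherence is part of the primary objective, and a count of aborts does not measure it. An abort needs a session to have begun. A participant who leaves the device in its box on a given day adds nothing to the count. Low adherence and perfect adherence can therefore give the same value, and a participant who tries every session can look worse than one who skips many.

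On safety the gap is narrower: the events are collected, but the statistical section does not say that their incidence will be estimated.

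Both quantities are needed for the randomized trial that Study objectives says this study is to prepare. Followed as written, the plan would deliver neither as a prespecified result.

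**Working it through.** **Inputs**
- Scheduled sessions: 28 daily and 9 taper (3 + 3 + 3), from the Visits section. 28 + 9 = 37 per participant.
- Missed-visit stop: more than 10, from Stimulation Stopping criteria.
- Sample size: 50, from Sample Size. 50 × 37 = 1,850 scheduled sessions.
- The plan states no adherence figure, so there is none to reproduce.

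**Step 1: what enters the count.** The statistical section does not define an abort. The Visits section describes it as a session started and then stopped, and lists it as a separate notice from a session not completed in its slot. On that reading, a session never started adds 0.

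**Step 2: lowest completion that does not trigger the missed-visit rule.** 37 − 10 = 27, and 27/37 = 73.0%. Among the 10 sessions not completed, the abort count can be anything from 0 (none started) to 10 (all started and stopped).

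**Step 3: participants side by side.** Missed sessions are taken as never started and not made up. The single abort is placed in the taper, where the text says it uses up one of the allowed sessions.

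| Participant | Completed | Completed/37 | Aborts |
|---|---|---|---|
| Attends all | 37 | 100% | 0 |
| Attempts all, aborts one | 36 | 97.3% | 1 |
| Skips 3 | 34 | 91.9% | 0 |
| Skips 10 | 27 | 73.0% | 0 |
| Stopped at the 11th miss | at most 26 | at most 70.3% | can be 0 |

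If all 10 skips fall in the daily phase, completion there is 18/28 = 64.3%, still with no aborts.

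**Step 4: the same at n = 50 (hypothetical).**
- Everyone aborts one: 50 × 36 = 1,800 completed, 1,800/1,850 = 97.3%, 50 aborts.
- Everyone skips 10: 50 × 27 = 1,350 completed, 1,350/1,850 = 73.0%, 0 aborts.
- Difference: 1,800 − 1,350 = 450 fewer completed sessions, with the lower abort count.

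**Step 5: a denominator alone does not cure it.** The design already implies 37. For the participant who skips 10, 0/37 = 0 and 0/27 started = 0. The numerator is the problem for adherence.

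**Step 6: what the added measures would give.** Completed/37 separates 73.0% from 100%. As examples of precision at n = 50 (Clopper-Pearson, two-sided 95%): 40/50 meeting a threshold gives 66.3% to 90.0%, and 0/50 with a serious adverse event gives an upper limit of 1 − 0.025^(1/50) = 7.1%. These show what 50 participants can support. They do not size the defect.

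**The case against.** **The data exist.** Staff follow adherence through completed sessions, the device sends notices, and adverse events are graded and reported to the IRB. A completion table and an adverse-event table could be made from these records at any time. This is true, and it makes the remedy cheap. But monitoring during conduct is not a planned analysis, and an IRB summary is not a prespecified estimate of incidence.

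**The abort count suits tolerability.** This stands. A session begun and then stopped is a reasonable sign of poor tolerance, and the plan sets no per-participant score or ranking. The count should be kept and given a denominator of sessions started. The gap is that nothing beside it measures adherence.

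**Equal zeros are not certain.** This also stands. If some of the 10 sessions were started and stopped, the count is between 1 and 10. The documents do not say whether a never-started session can be made up: the visit table ends stimulation on day 55, while the text below it runs the taper to day 60. Nor do they say whether an abort counts as missed under the stopping rule. The claim is only that the two participants can score alike.

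**Non-compliance withdrawal.** The investigator may withdraw a participant who skips many sessions before the eleventh miss. That would be recorded ("Reasonable attempts will be made by the investigator to provide a reason for study subject withdrawals"), but it would still not change the abort count.

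**Other feasibility data are collected.** A caregiver skills test is scheduled on day 5, and evaluation forms are listed. These bear on proficiency and acceptability. They do not show how many sessions were delivered, and no analysis of them is stated.

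**It is a pilot.** The disclaimer about significance concerns the efficacy test. Feasibility is the stated purpose of this study.

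**Conclusion.** The point holds. The stated measure cannot show adherence: 27/37 (73.0%) can record the same zero aborts as 37/37, and 36/37 with one abort records more than either. The statistical section plans no adherence analysis and no adverse-event table, although both belong to the primary objective.

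This rests on three assumptions: an abort requires a started session, as the Visits section describes; the sessions in the example were never started; and they were not made up. How often this will happen cannot be known from the documents, and the n = 50 cases only illustrate how the measure behaves.

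A reader might infer more than this, and the documents do not support it:
- That the trial fails to record adherence or adverse events. It captures both.
- That safety has no outcome in the statistical section. CogState is named there.
- That any participant at 27/37 must score zero, or is sure to continue. Neither is assured.
- That the abort count is invalid and should be dropped. It is usable for tolerability.

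**What to change.** In Statistical Methods and Analysis, Primary:

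1. Keep aborts as a tolerability measure: aborted sessions over sessions started.
2. Add adherence for every enrolled participant: completed sessions/37 scheduled, and completed/28 for the daily phase, from the device notices. Tabulate aborted, never-started and post-discontinuation sessions separately. Report the median and IQR, and the proportion meeting a threshold that the sponsor prespecifies and justifies, with an exact 95% confidence interval.
3. Add safety: number and proportion of participants with any adverse event (by severity and relatedness) and with any serious adverse event, with exact 95% confidence intervals, alongside CogState.
4. State whether an aborted session counts as missed under the stopping rule, and whether a never-started session can be made up.
5. Reconcile the length of the daily session. The text on daily sessions gives 20 minutes, while the visit table and the device prompt give 30. Until these agree, a completed session has no single meaning.

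Cost: protocol and SAP wording, one sponsor decision on the threshold, a few extra tables, and possibly one added field for the reason a session was missed or aborted. The session notices and graded adverse events are already collected.
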